**Varenicline.** All participants will be evaluated by the study physician, and prescribed varenicline (if eligible). Individuals with a history of seizures, allergic reaction to varenicline, endorse current suicidality, and/or those who are pregnant, planning to become pregnant, or breastfeeding will be excluded from the proposed study. As a precaution, individuals who report current cardiovascular disease will require clearance from the study physician or their personal physician to use varenicline. Notably, recent research has indicated that neither varenicline nor NRT increases the risk of serious cardiovascular events. In December 2016, the FDA lifted the boxed warning for varenicline after findings were published from a large clinical trial showing that the risk of neuropsychiatric adverse events associated with varenicline did not differ from the nicotine patch or placebo, and that varenicline was more effective for smoking cessation than the nicotine patch, bupropion, and placebo (the nicotine patch and bupropion were more effective than placebo). As a precaution, female participants will be advised to avoid pregnancy while taking varenicline and to discontinue the medication should they become pregnant. However, the findings of observational research suggests that taking varenicline does not appear to be harmful during pregnancy. During the first (pre-quit) week of the study, participants will continue smoking and begin taking varenicline. Doses are titrated during the first week of medication (days 1-3: 0.5 mg once daily; days 4-7: 0.5 mg twice daily).

**Oral NRT.** Participants randomized to a VAR+N group will be provided with a supply of 2mg/4mg nicotine lozenges or 2mg/4mg gum (depending on participant preference) and instructed to use a piece as directed after they quit smoking, especially when they have the urge to smoke. Participants will be instructed to chew a piece of gum as follows:

Baseline: every 1-2 hours (12-24 per day)

4-Weeks Post-Quit: every 1-2 hours (12-24 per day), and to begin reducing to at least every 2-4 hours (6-12 per day)

8-Weeks Post-Quit: every 2-4 hours (6-12 per day), and to begin reducing to at least every 4-8 hours (3-6 per day)

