Additional supply of gum or lozenges will be provided during in-person visits or through the mail. Participants assigned to VAR+N with medication reminders will receive smartphone prompts (through the Insight™ app) (during waking hours) reminding them to use a piece of gum or a

lozenge every 3 hours through 4 weeks post-quit, every 4 hours during post-quit weeks 5-8, and every 6 hours during post-quit weeks 12.

Reminders. Participants assigned to the reminder groups will receive reminders to take varenicline and/or oral NRT as follows:

Varenicline Reminders. Participants will receive varenicline reminders that correspond with the medication schedule. The reminders will provide a message and then ask the participant if they have taken medication. Reminder 2 will only appear if the participant has reported “no” to reminder 1. Reminder 3 will only appear if the participant has reported “no” to reminder 2. On the 3rd reminder the participant will be asked why they did not take their medication.

Pre-Quit Day 1: Only PM reminder (1 white pill (0.5 mg) daily)

Pre-Quit Days 2-3: Only AM reminder (1 white pill (0.5 mg) daily)

Pre-Quit Days 4-7: AM and PM reminders (1 white pill (0.5 mg) in the morning and 1 in the evening)

Day 8 to end of treatment: AM and PM Reminders (1 blue pill (1 mg) in the morning and 1 in the evening)

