**Table 3. NRT reminders**

1. Don't forget to use nicotine gum/lozenges regularly throughout the day! It is recommended that you use a piece of gum/lozenge every 1-2 hour.
 
After you have been smoke free for 6 weeks, taper down to using a piece of gum/lozenge every 2-4 hours and then after being smoke free for 8 weeks, taper down to a piece every 4-8 hours.
	
2.	Have you used a piece of gum/lozenge within the past 2 hours?  No Yes
3.	(If 2 = No) Have you used a piece of gum/lozenge within the past 4 hours?  No Yes
4.	(If 3 = No) Have you used a piece of gum/lozenge within the past 8 hours?  No Yes

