**Figure 1: Study Timeline**

Developing a Quit Plan. At baseline, eligible participants will meet with a tobacco cessation counselor who will provide an overview of the tobacco cessation program, and help participants to set and prepare for their quit date. Participants will be asked to quit smoking the evening prior to their next weekly appointment (Visit 2).

Counseling. Participants will complete counseling session in-person or remotely with a Tobacco Treatment Specialist at the baseline visit and each visit through 4 Weeks Post-Quit. The counselor will check in with participants about the difficulties and successes they have experienced, and plan for any challenging situations that are anticipated. Advice and support will be provided as needed. Topics will include 1) the impact of tobacco on health/benefits of quitting, 2) stress management strategies, 3) making positive lifestyle changes, 4) developing

coping skills, and 5) relapse prevention. The counselor will check in with participants each week about the difficulties and successes they have experienced, and plan for any challenging situations that are anticipated.

Compensation. Participants will receive a \$20 payment for completion of the Baseline visit, Quit Day, 4 Weeks Post-Quit, 8 Weeks Post-Quit, 12 Weeks Post-Quit, and 26 Weeks Post-Quit. (see Table 4 for study compensation schedule). In addition, participants will receive up to \$10 weekly for completing the daily smartphone assessments. Specifically, they will receive \$10 for completing at least 6 out of 7 EMAs, and \$5 for completing at least 4 out of 7 EMAs each week. Participants who complete 3 or fewer EMAs will not receive additional compensation. Participants may earn up to \$250 for participation in the study.

Discontinuing Reminders, Varenicline, or NRT. Using the following guidelines a participant may continue in the study if: 1) they no longer wants to receive reminders via the app, we will disable app reminders, 2) they no longer wants to take varenicline, we will have them delete the app, but will still ask that they come in to the clinic for in-person visits for follow-up, 3) they no longer wants to take NRT, they will be asked to answer that they didn't chew gum on the EMAs.

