**Scheduled EMAs.** The EMA methodology used in this study will be similar to what was used in our previous studies, and by other researchers. All participants will download the study app onto their personal or study-provided phone and will be asked to complete scheduled EMAs once a day for 13 weeks. The scheduled EMAs will be prompted by the smartphone app, 30 minutes after the participant's scheduled wake time. The phone will ring and vibrate to cue these EMAs for 30 seconds. If the participant has not responded after 5 prompts, the assessment will be rescheduled and will be prompted again (e.g., 15 minutes later). This process will continue until the participant acknowledges the prompt, or the assessment is recorded as missed (i.e., 4 prompts spaced 15 minutes apart). These EMAs will ask questions about current and past 24-hour thoughts, feelings, experiences, behaviors (e.g., smoking lapses), physical symptoms, and medication adherence.

**Programming.** The mHealth Shared Resource at the OUHSC and Stephenson Cancer Center (SCC) offers resources that empower researchers to build, test, and launch technology-based assessment and intervention tools. The mHealth resource employs a program manager and 3 senior programmers who develop and maintain web and mobile applications and relational databases. Applications are developed using state-of-the-art cross-platform design tools. The Insight™ platform has already been developed and is being used by the OTRC investigators in other studies. The platform will allow the project investigators to quickly set up scheduled EMAs and messaging that are unique to the proposed study.

**Smartphone application training.** As in all of our studies, participants will watch a brief step-by-step video tutorial (created by the researchers) at the baseline visit that demonstrates use of all app features and participants will receive hands-on training. This training approach has minimized participant difficulties in our past research.

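### The rule for stopping oral NRT prescribes a gum-only EMA answer instead of asking for actual use, and does not say what happens to the NRT prompts

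*Combined protocol and SAP*

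**What the plan says.** The paragraph on discontinuing reminders, varenicline or NRT (Section C, after Compensation) lists three situations in which a participant may stay in the study.

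- Item 1: if "they no longer wants to receive reminders via the app, we will disable app reminders".
- Item 2: if "they no longer wants to take varenicline, we will have them delete the app", while clinic follow-up continues.
- Item 3: if "they no longer wants to take NRT, they will be asked to answer that they" had not chewed gum, this being the answer for the EMAs.

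Other parts of Section C bear on item 3.

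- Oral NRT: VAR+N participants receive a "supply of 2mg/4mg nicotine lozenges or 2mg/4mg gum (depending on participant preference"), to be used after quitting and especially when there is an urge to smoke.
- Reminders: "Participants assigned to VAR+N with medication reminders will receive smartphone prompts" about NRT through week 12. Table 3 shows the message, which tells them "to use nicotine gum/lozenges regularly throughout the day" and then asks about gum or lozenge use in the past 2, 4 or 8 hours.
- Scheduled EMAs, once a day for 13 weeks: "These EMAs will ask questions about current and past 24-hour thoughts, feelings, experiences, behaviors (e.g., smoking lapses), physical symptoms, and medication adherence".

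The Abstract names EMA as a tool for measuring medication adherence. Aim 2 makes pharmacotherapy adherence an outcome.

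**The concern.** Item 3 turns a measurement into a standing reply. A participant who has stopped NRT is not asked what was used that day; the answer is supplied in advance. Someone who later takes a piece during a craving, which is the situation the product is meant for, would be recorded as a non-user. A lozenge user could give the prescribed answer truthfully and still be using NRT.

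Oral NRT is what separates the two drug arms. Section A notes that infrequent gum use in earlier bupropion-plus-gum trials made any added benefit of oral NRT hard to judge. A pilot with that background needs to know how much NRT was actually taken. Hidden use would probably fall on high-craving days, so it could also distort any relation between NRT use, withdrawal, side effects and cessation examined under Aim 3.

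The second gap is procedural. In the VAR+N + Reminders cell, stopping NRT triggers no stated change to messages that urge its use. The one rule about switching reminders off does not distinguish the two drugs.

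**Working it through.** There is no figure in the plan to reproduce. The check sets the passages side by side and counts who and what each part can reach.

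**Who can be affected**

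- Planned sample 100 (Abstract); half receive oral NRT (Study Design). Reach of the prescribed EMA answer: 100 / 2 = about 50.
- NRT prompts go only to VAR+N with reminders. Reach: 100 / 4 = about 25, assuming equal allocation to the reminder factor, for which no ratio is stated.
- No stopping rate is given. At an assumed 10% to 30%, the prescribed answer reaches 0.10 × 50 = 5 to 0.30 × 50 = 15 participants. The prompt question reaches 0.10 × 25 = 2.5 to 0.30 × 25 = 7.5, and fewer if some ask for reminders to be disabled.

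**How many daily answers are prescribed**

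The EMA covers 13 weeks: 1 pre-quit and 12 post-quit. After a stop at the end of post-quit week w, 7 × (12 − w) daily answers remain:

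- w = 2: 7 × 10 = 70
- w = 4: 7 × 8 = 56
- w = 8: 7 × 4 = 28

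If NRT is used again on d of those days and the instruction is followed, the EMA shows 0 and understates use by d days. The documents do not allow d to be estimated.

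**What the other sources add**

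- After a stop at week 2, questionnaires fall at weeks 3, 4, 8 and 12 within the treatment period: at most 4 occasions against 70 daily records. The plan does not say at which of them adherence is asked.
- Staff follow-up of NRT use appears under Medication Risk Management (Section F), with no stated link to the adherence outcome.
- The Table 3 questions record gum or lozenge use, but only in the VAR+N + Reminders cell. They give no comparable measure in VAR+N without reminders, which is the comparison Aim 2 needs for NRT. Whether they count as EMAs under item 3 is not stated.

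**Direction of the error**

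Prescribed zeros can only lower EMA-recorded NRT use. If later use is equally common with and without reminders, the level is too low by the same amount in both and the difference is preserved. If reminders bring some participants back to NRT, the zeros hide that effect and shrink the Aim 2 contrast. The plan gives no basis for choosing between these.

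**Prompts after a stop, for illustration**

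The interval is 3 hours to week 4, 4 hours in weeks 5–8 and 6 hours in weeks 9–12. With 16 waking hours (assumed), that is about 5, 4 and 2 prompts a day after rounding down. For someone who does not ask for reminders to be disabled:

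- stop at end of week 2: 5 × 14 + 4 × 28 + 2 × 28 = 70 + 112 + 56 = 238
- stop at end of week 4: 112 + 56 = 168
- stop at end of week 8: 56

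**The case against.** The strongest reply is that item 3 is loosely worded but harmless. It applies only once a participant no longer wants NRT, when a report of no use is normally true. Read beside item 2, its evident purpose is to keep these people in the study and answering EMAs. Nothing tells anyone to deny later use. Gum may be shorthand: the dosing schedule is also written in terms of gum for both products, and Table 3 asks about both. The EMA items themselves are not in the documents. Much of this stands. It limits the size of the problem, but it does not change what the instruction says, and asking for actual use would serve the same purpose.

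A reader might infer several stronger things that the documents do not support.

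- *That nothing can switch the NRT prompts off.* Item 1 disables reminders on request, and item 2 removes the app. The gap is that neither is tied to stopping NRT. Nor does the plan say that disabling is all-or-nothing; it simply does not separate the two drugs.
- *That NRT exposure data as a whole are fixed by instruction.* Only EMA answers after a stop are prescribed. The questionnaire and staff follow-up are not.
- *That the app will go on urging NRT on anyone who stops, including after side effects.* Prompts reach one cell of four. Item 3 concerns a participant's wish, and Section F gives the study physician and staff responsibility for side effects and adverse events.
- *That participants keep their NRT supply after stopping.* The plan does not say whether it is kept or returned.

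**Conclusion.** The concern holds in a limited form. As written, item 3 replaces a daily observation with a prescribed gum-only answer, so any later gum or lozenge use is recorded as zero in a named adherence source for Aim 2. It can reach up to about 50 participants, for 28 to 70 daily answers each in the stop times worked above. The number actually affected depends on a stopping rate and a rate of later use that the documents do not give, so the size of any bias cannot be stated.

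The primary analysis is not touched: CO-confirmed abstinence is modelled by assigned drug and reminder condition with baseline-type covariates (Section D), and the EMA answer on NRT does not enter it.

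The silence on prompts is a separate and smaller gap, confined to about 25 participants if allocation is equal. The prompt counts are illustrations that rest on 16 waking hours, the chosen stop times and no request to disable reminders. Overall this is a cheap improvement, not a flaw that threatens the trial.

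**What to change.** Replace the prescribed answer in item 3 with wording such as: *participants who stop NRT continue the EMA and report any gum or lozenge use each day as it occurred*. Record the date and the reason for stopping NRT. This changes data collection only. It costs one sentence and a short stop record (date and reason), and adds no assessment, because these participants are already asked to complete the daily EMA.

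Separately, reconcile the reminder passages (Oral NRT, Reminders, Table 3) with the discontinuation paragraph, so that the protocol states what happens to each reminder type when NRT is stopped and whether the Table 3 questions count as EMAs. What that rule should be is for the sponsor to decide. Any programming cost depends on whether the app can handle the two reminder types separately, which the documents do not say.

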### **Study Measures.**

Screening Measures (online or over the phone). Screening data will be collected using the secure web-based REDCap platform, which provides an intuitive user interface that streamlines project development and improves data entry through real-time validation rules. The initial online screening will include assessment of demographics, smoking history, readiness to quit, and other eligibility criteria.

Traditional Questionnaire Measures. Questionnaire data, including measures of tobacco/health history, sociodemographic characteristics, nicotine dependence, withdrawal symptom severity, depression, perceived stress, mental health, beliefs about medications, medication adherence, and self-efficacy will be collected via REDcap on tablet computers. The amount of time needed for participants to complete the computer-administered questionnaires varies by study visit. It is estimated that the longest visit (baseline) will require one hour to complete. We have found that even individuals with no experience using computers have had few problems completing study assessments. The questionnaire appendix will come from the TTRP IRB 6951.

Biological/Anthropometric Measures. Expired CO levels will be measured at each visit either in-person using the portable Vitalograph ecolyzer or remotely using the Bedfont iCO smokerlyzer which will interface the Insight™ smartphone application. Please note that the Insight™ smartphone application has integrated automated and secure (i.e., encrypted) facial recognition software to ensure that only the participant provides a CO breath sample. Self-reported abstinence from smoking will be verified with a CO level of ≤ 6 ppm at all subsequent post-quit visits. Body Mass Index (BMI) will be calculated (kg/m^2) based on height and weight measurements collected at the baseline visit.

**Ecological Momentary Assessment (EMA).** EMA can accurately measure phenomena in real-time, natural settings. EMA items will identify fluctuations in key variables that predict study outcomes with less bias than traditional in-person assessments.

**Scheduled EMAs.** The EMA methodology used in this study will be similar to what was used in our previous studies, and by other researchers. All participants will download the study app onto their personal or study-provided phone and will be asked to complete scheduled EMAs once a day for 13 weeks. The scheduled EMAs will be prompted by the smartphone app, 30 minutes after the participant's scheduled wake time. The phone will ring and vibrate to cue these EMAs for 30 seconds. If the participant has not responded after 5 prompts, the assessment will be rescheduled and will be prompted again (e.g., 15 minutes later). This process will continue until the participant acknowledges the prompt, or the assessment is recorded as missed (i.e., 4 prompts spaced 15 minutes apart). These EMAs will ask questions about current and past 24-hour thoughts, feelings, experiences, behaviors (e.g., smoking lapses), physical symptoms, and medication adherence.

**Programming.** The mHealth Shared Resource at the OUHSC and Stephenson Cancer Center (SCC) offers resources that empower researchers to build, test, and launch technology-based assessment and intervention tools. The mHealth resource employs a program manager and 3 senior programmers who develop and maintain web and mobile applications and relational databases. Applications are developed using state-of-the-art cross-platform design tools. The Insight™ platform has already been developed and is being used by the OTRC investigators in other studies. The platform will allow the project investigators to quickly set up scheduled EMAs and messaging that are unique to the proposed study.

**Smartphone application training.** As in all of our studies, participants will watch a brief step-by-step video tutorial (created by the researchers) at the baseline visit that demonstrates use of all app features and participants will receive hands-on training. This training approach has minimized participant difficulties in our past research.

**Data loss prevention.** In order to overcome potential loss of data, phones will be programmed to connect to our secure server to upload encrypted data every 1.5 hours. This will ensure that no collected EMA data are lost. This tactic will also allow the researchers to remotely monitor each participant's EMA completion rate and intervene (e.g., call the participant) when this rate is low. Importantly, EMA data are password protected and encrypted on the phone and only encrypted data are transmitted to our secure server. Thus, study data are ONLY accessible by the research team. In addition, all study data can be remotely wiped from phones once the study is completed.

**EMA alert settings.** At the baseline visit, a phone set-up wizard is used to set participant sleep and wake times for each day of the week. This practice reduces the likelihood that the phone will ring when participants are sleeping. In addition, participants may delay EMAs by up to 20 minutes (i.e., by clicking the snooze assessment option when an EMA is pushed).

#### **D. Statistical Methods**

All questionnaires will be scored using methodology described in the published literature. Sociodemographic information will be summarized using frequencies with associated percentages (categorical/binary outcomes) or means with standard deviations (continuous outcomes). The 2x2 factorial design will be evaluated using logistic regression models, where

smoking status (12 or 26 weeks post-quit date) is included as the dependent variable. The dichotomous variables, medication type (NVAR vs. VAR) and message reminder type (medication reminders vs. no reminders), will be included as independent variables, as well as the interaction term. Sociodemographic covariates and nicotine dependence will be included in the model as covariates. Generalized Linear Mixed Models (GLMM) will be used to examine the influence of EMA variables that are measured repeatedly and are therefore correlated within subjects. The PROCESS macro for SPSS/SAS (described in Hayes, 2013 and available online) will be used to conduct mediation analyses with the goal of identifying variables (e.g., withdrawal symptom severity) that mediate the relation between treatment condition and smoking cessation outcomes. This method uses an ordinary least squares path analytic framework to estimate direct and indirect effects in single and multiple mediation models, and bootstrapping methods are incorporated to generate confidence intervals. The data collected in the proposed study will provide preliminary information for future external funding applications.

